- Eosinophilic intranuclear inclusion bodies (EIIBs) were observed in the proximal tubule epithelium of the kidneys at doses of ≥10 mg/kg/day in rats. The EIIBs were not accompanied by apparent necrosis, inflammation, or impaired renal function and were not considered adverse. Similar findings have been reported in the literature and are considered to be species-specific to the rat [19]. Elevated creatinine levels were not reported in the TAK-831 clinical studies summarized above; creatinine will continue to be measured in the clinical studies.
- Postural hypotension and dizziness were observed in prior TAK-831 studies in healthy subjects. However, the incidence of dizziness in subjects treated with TAK-831 and placebo was similar. Subjects will be informed of these findings and possible ways to mitigate this risk, and orthostatic vital sign assessments will be monitored periodically at study visits.
- Study procedure–specific risks include issues relating to blood collection for safety assessment/PK monitoring (venipuncture may cause discomfort at the site of puncture; bruising and swelling; and rarely, infection or faintness from the procedure), and the placement of ECG pads, which may cause some local redness and/or erythema/itching. The PD assessments planned for the study, aside from those requiring a blood draw, are noninvasive and are associated with minimal risk.

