9.1.7 Vital Sign Procedure

Vital signs will include body temperature, blood pressure (systolic and diastolic), and pulse (bpm). Supine blood pressure, and pulse will be collected at a subset of study visits as outlined in the Schedule of Study Procedures (Appendix A). All other vital signs assessments will be collected in a sitting position.

Body temperature will be measured with an oral (temperature taken at floor of the mouth), tympanic, or infra-axillary thermometer. The same method (eg, oral, tympanic, or infra-axillary) must be used for all subsequent measurements for each individual subject and should be the same for all subjects.

Subjects should rest in the specified position for at least 5 minutes prior to blood pressure and pulse measurements. The same method (eg, same size cuff, manual or automated) must be used for all measurements for each individual subject and should be the same for all subjects. It is also recommended that the same arm be used for all blood pressure measurements for each individual subject.

Pulse should be recorded separately and should not be derived from the ECG.

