- ^g Supine blood pressure and pulse will be measured at screening (Visit 1), Day 1 (Visit 3), Day 42 (Visit 7), and Day 84/ET (Visit 10); sitting blood pressure and pulse will be measured at all other scheduled time points.
- ^h Height and BMI will be collected at screening (Visit 1) only.
- ⁱ Hematology, serum chemistry, and urinalysis. Clinical laboratory blood samples will be collected after a 6-hour fast, with the exception of screening (Visit 1) when fasting is not required. Antipsychotic serum blood levels may be retested at investigator's request.
- ^j Women of childbearing potential only. Serum hCG test will be performed at screening (Visit 1) and safety follow-up (Visit 11). Urine hCG tests will be performed at all other scheduled time points. The hCG test can be repeated at any time at the investigator's discretion.
- ^k May be repeated at any time at the investigator's discretion.
- ¹ Efforts should be made to perform the BACS assessment at approximately the same time of day throughout the study (postbaseline assessments must be administered ±2 hours from the time of baseline assessment administration).

ⁿ On Day -14 (Visit 2), 1 PD sample will be collected. On Day 1 (Visit 3), 1 PK blood sample and 1 PD blood sample will be collected predose. On Day 28 (Visit 6), subjects will take study drug at the site after predose PK and PD blood samples have been collected, and repeat PK and PD blood samples will be collected at the end of the visit. On Day 42 (Visit 7), Day 56 (Visit 8), and Day 84/ET (Visit 10), 1 PK blood sample and 1 PD blood sample will be collected at each visit; the subject will take study drug at the usual time in the morning before each of these 3 visits. For Days 42 and 56, it is recommended that sites schedule the clinic visit at different times of the day: 1 visit in the morning and 1 visit in the afternoon. It is recommended that the Day 42 Visit be scheduled in the afternoon because the subject does not have to fast for safety laboratory assessments. The actual date and time of each PK blood sample collection, time since last dose was administered, and time since last meal will be recorded on the source document and eCRF.

P Study subjects will be instructed to take their study drug QD in the morning with water or milk; subjects should avoid drinking juices 1 hour before and 1 hour after taking study drug.

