5.1.3 Safety Endpoints

- Percentage of subjects who experience at least 1 TEAE.
- Percentage of subjects who meet the markedly abnormal criteria for safety laboratory tests at least once postdose.
- Percentage of subjects who meet the markedly abnormal criteria for vital sign measurements at least once postdose.
- Percentage of subjects who meet the markedly abnormal criteria for safety electrocardiogram (ECG) parameters at least once postdose.
- Percentage of subjects with treatment-emergent suicidal ideation or suicidal behavior as measured using the C-SSRS.

TAK-831-2002 Statistical Analysis Plan Amendment No. 1

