7.12.3 Vital Signs

Descriptive statistics (N, mean, SD, median, minimum, and maximum) will be used to summarize vital sign parameters at baseline, each post-baseline visit, and change from baseline to each post-baseline visit. Only observations within 3 days of the study drug will be included in the tables.

Vital sign MAVs, identified by the criteria defined in Appendix B, will be tabulated. If a subject has a MAV for a particular vital signs parameter, all visits for that subject for that parameter will be listed. The number and percentage of subjects with at least 1 postdose markedly abnormal vital signs measurement will be summarized. The mapping of the subjects who meet the MAV criteria will be listed as a table. All observations, including ones at unscheduled visits, will be included in the MAV evaluation and summaries.

Orthostatic hypotension, identified by the criteria defined in Appendix C, will be calculated at every time point where standing and supine measurements are available using the formula: standing vital measurement – supine vital measurement. The mapping of the subjects who meet the criteria for orthostatic hypotension will be listed by study visit as a table. All orthostatic hypotension observations, including ones at unscheduled visits, will be included in the subject mappings.

Listings of all vital signs data will be provided in Appendix 16.2. Vital sign MAVs will be flagged in the listings. The listing will include site number, subject identifier, age, gender, treatment group, study visit, and sample collection date.

7.12.4 12-Lead ECGs

Descriptive statistics (N, mean, SD, median, minimum, and maximum) of ECG parameters, including heart rate, PR interval, RR interval, QRS interval, QT interval, and QTc interval (Fredericia's and Bazett's corrections), will be presented for baseline, each post-baseline visit, and change from baseline to each post-baseline visit. Only the scheduled measurements will be included in the summary. Only observations within 3 days of the study drug will be included in the tables. No inferential statistics will be presented.

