Appendix B Criteria for Abnormal Changes from Baseline of Vital Signs

Appendix C Criteria for Identification of Markedly Abnormal Orthostatic Changes

Parameter	Criteria
Orthostatic Hypotension	(Orthostatic Systolic Blood Pressure < -20 mm Hg OR
	Orthostatic Diastolic Blood Pressure < -10 mm Hg) AND Heart Rate Increase > 20 beats/min

Note: Orthostatic measurement = standing vital measurement – supine vital measurement.

Parameter	Lower Criteria	Upper Criteria
Heart rate	< 50 beats per minute	>120 beats per minute
PR	≤80 milliseconds	≥200 milliseconds
QT Interval	≤300 milliseconds	≥460 milliseconds
QTcB Interval	≤300 milliseconds	≥500 milliseconds OR
		≥30 milliseconds change from baseline and ≥450 milliseconds
QTcF Interval	≤300 milliseconds	≥500 milliseconds OR
		≥30 milliseconds change from baseline and ≥450 milliseconds
QRS	≤80 milliseconds	≥180 milliseconds

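### Orthostatic hypotension is derived as standing minus supine, but the protocol schedules no standing reading, so on the written schedule an empty output could be misread as no cases

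*SAP*

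**What the plan says.** Protocol 4.3 (Benefit/Risk Profile) reports postural hypotension and dizziness in earlier healthy-volunteer studies. Among its mitigation measures it says that "orthostatic vital sign assessments will be monitored periodically at study visits". It gives no posture and no visit.

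SAP 7.12.3 takes up the topic. Orthostatic hypotension is the standing value minus the supine value and "will be calculated at every time point where standing and supine measurements are available". SAP Appendix C repeats the formula and sets the flag: a fall of more than 20 mm Hg systolic or more than 10 mm Hg diastolic, together with a heart rate rise of more than 20 beats/min. The stated output is a subject mapping: "The mapping of the subjects who meet the criteria for orthostatic hypotension will be listed by study visit as a table". No count or percentage by arm is stated for it.

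Two places in the protocol set the posture. Section 9.1.7 assigns supine blood pressure and pulse to some visits and then says: "All other vital signs assessments will be collected in a sitting position". Appendix A footnote g names Visits 1, 3 and 7 for supine readings and completes the list with "and Day 84/ET (Visit 10); sitting blood pressure and pulse will be measured at all other scheduled time points". Neither place mentions standing.

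**The concern.** The plan names a risk, promises to monitor it and defines a derived variable for it, but the schedule never collects one of the two readings that the variable needs. The SAP rule depends on availability, so it runs without error on no data and returns an empty mapping.

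An empty mapping looks the same whether nobody was affected or nobody was measured. In a study report, the second could pass for the first, on a risk that the sponsor itself singled out.

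Adverse event tables may not fill the gap. Protocol 4.1.3 says that one of 15 subjects in TAK-831-1004, and two in each cohort of eight in TAK-831-1005, met orthostatic criteria without a dizziness event being reported. These are few subjects, and other event terms are possible, so this shows only that the measurement and the symptom report can diverge.

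**Working it through.** The plan gives no figure to reproduce here. The check is a count of scheduled readings by posture.

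**Inputs.** Vital signs are taken at all 11 visits (Protocol Appendix A). Posture comes from footnote g and section 9.1.7.

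| Posture | Visits | Number |
|---|---|---|
| Supine | 1 (screening), 3 (Day 1), 7 (Day 42), 10 (Day 84/ET) | 4 |
| Sitting | 2, 4, 5, 6, 8, 9, 11 | 7 |
| Standing | none | 0 |

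The total is 4 + 7 + 0 = 11, so every visit is accounted for. No visit is in two rows.

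**Scheduled pairs now.** Visits with both a supine and a standing reading: 0 of 11. The SAP derivation has no scheduled input.

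**Scheduled pairs after the fix.** A standing reading after each supine one gives 4 pairs per subject. The first double-blind dose is given at the end of the Day 1 visit (Protocol 8.1.3 and Appendix A footnote b), so Visits 1 and 3 are predose. Of the 8 visits after the first dose (Visits 4 to 11), 2 would have a pair: Visits 7 and 10.

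**What a zero would then mean.** With no events among n subjects assessed, the exact two-sided 95% upper limit for the true rate is 1 − 0.025^(1/n). Planned arm sizes are 52 per dose and 78 on placebo (Protocol 2.0).

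- One dose, n = 52: 1 − 0.025^(1/52) = 6.8%
- Placebo, n = 78: 1 − 0.025^(1/78) = 4.6%
- All doses, n = 3 × 52 = 156: 1 − 0.025^(1/156) = 2.3%
- One dose if only half the subjects have a postdose pair (an assumption), n = 26: 1 − 0.025^(1/26) = 13.2%

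With n = 0, as on the written schedule, the limit is 100%: the empty mapping excludes no rate at all. The denominator is what tells these cases apart, and the stated mapping has none.

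**The case against.** The strongest reply is that the SAP sentence is sound. It is conditional, it allows for unscheduled observations, and it works on whatever data exist. Protocol 4.3 tells sites that orthostatic signs will be monitored, so some may have taken standing readings outside the schedule. The fault would then be an inconsistency within the protocol, not a faulty analysis. This stands in part. The inconsistency does start in the protocol, and emptiness is certain only on the written schedule. But ad hoc readings, with no stated time after standing, are a poor basis for a promised mitigation, and the SAP still does not say what to report if there are none.

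The reply also points out that much safety information remains. Adverse events are tabulated, vital signs are summarized and listed by treatment group, no adverse events of special interest are named, and Protocol 4.3 says dizziness was similar on TAK-831 and placebo. This stands and keeps the point minor.

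A protocol change may also come late, since SAP Amendment 1 is dated 01 February 2021. The documents do not say how many visits remain. The SAP wording can be changed either way.

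A reader might infer three stronger things that the documents do not support:

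- **That the heart rate condition is an error.** Appendix C does require both parts: "Orthostatic Diastolic Blood Pressure < -10 mm Hg) AND Heart Rate Increase > 20 beats/min". A large pressure fall with a pulse rise of 15 would go unflagged. But the appendix is headed as criteria for markedly abnormal changes, so the compound rule may be deliberate, and the documents give no basis for estimating how many falls it would miss.
- **That orthostatic events are wrongly left out of a safety endpoint.** The endpoint is "Percentage of subjects who meet the markedly abnormal criteria for vital sign measurements at least once postdose", and SAP 7.12.3 says: "Vital sign MAVs, identified by the criteria defined in Appendix B, will be tabulated". Orthostatic hypotension has its own paragraph and its own output. The natural reading is that Appendix C events are not meant to count in that percentage.
- **That the earlier studies give a drug rate.** Their criteria are not stated. The TAK-831-1005 data were blinded, included placebo subjects and came with CSF catheterization. They should not be pooled with a single-dose crossover study to predict events here.

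**Conclusion.** The point holds as a mismatch between promise, derivation and schedule: 0 of 11 visits have a scheduled standing reading, so the SAP's orthostatic variable has no scheduled input. This rests only on Protocol 9.1.7 and Appendix A footnote g, which agree with each other and are readable in full. Whether sites took standing readings anyway cannot be known from the documents.

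The consequence is limited to safety reporting. An empty mapping could be read as evidence of absence when it carries no information. The efficacy conclusions are unaffected. The change is worth making because it is cheap and concerns a risk that the protocol itself names.

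**What to change.** **Protocol 9.1.7 and Appendix A footnote g.** Add a standing blood pressure and pulse at one fixed time after the supine reading at Visits 1, 3, 7 and 10, for visits still to come. Record the time since dose at Days 42 and 84/ET. It will vary: footnote n recommends an afternoon visit on Day 42, and section 8.1.3 allows non-morning dosing with approval. Footnote n already has time since last dose recorded with the PK sample at both visits, so this adds little work.

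**SAP 7.12.3.** Keep the mapping. Add the number and percentage of subjects by arm who meet Appendix C at least once postdose, with subjects who have a postdose standing and supine pair as the denominator. If no pairs exist at database lock, state that orthostatic hypotension was not assessed and omit the empty mapping.

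**Optional.** A second row for the pressure part alone, with the SAP's own cutoffs, would be informative but does not correct an error. It would raise background counts in every arm, placebo included.

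**Cost.** One short extra reading per supine visit, a protocol amendment that helps only remaining visits, and one descriptive table. If no visits remain, only the SAP wording changes.

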7.12.5 Other Observations Related to Safety

The modified Simpson Angus Scale and C-SSRS will be summarized at all time points for each treatment group and TAK-831 total and overall total using descriptive statistics.

7.13 Interim Analysis

An interim analysis for futility may be performed during the study, allowing for early study termination if the probability of success on the primary endpoint fails to meet a pre-specified criterion. The specifics of this analysis will be included in an interim analysis plan that will be finalized before interim unblinding.

7.14 Changes in the Statistical Analysis Plan

Considering the potential impact of noncompliant subjects, a supportive analysis on the primary endpoint based on PPS described in section 7.9.1 is added.

Section 7.2.5 is updated to provide details on site pooling method.

A separate listing for protocol deviations due to COVID-19 is added.

In section 7.9.2, clarification is added to describe the analyses on BNSS total (12-item, excluding item 4) and BNSS total (13-item).

Typographical errors are corrected.

Appendix A Criteria for Identification of Markedly Abnormal Laboratory Values Hematology—Criteria for Markedly Abnormal Values

Parameter	Unit	Low Abnormal	High Abnormal
Hemoglobin	Both	$< 0.8 \times LLN$	> 1.2 × ULN
Hematocrit	Both	$< 0.8 \times LLN$	> 1.2 × ULN
RBC count	Both	$< 0.8 \times LLN$	> 1.2 × ULN
WBC count	Both	<0.5 x LLN	>1.5 x ULN
Platelet count	Conventional	$<75 \text{ x } 10^{3}/\mu\text{L}$	>600 x 10 ³ /µL
	SI	<75 x 10 ⁹ /L	>600 x 10 ⁹ /L

LLN=lower limit of normal, RBC=red blood cell, ULN=upper limit of normal, WBC=white blood cell.

Serum	Chemistry-	Criteria	for Ma	rkedly	Abnormal	Values
	•/			•		

Parameter	Unit	Low Abnormal	High Abnormal
ALT	Both		>3x ULN
AST	Both		>3x ULN
GGT	Both		>3x ULN
Alkaline phosphatase	Both		>3x ULN
Total bilirubin	Conventional		>2.0 mg/dL
	SI		>34.2 µmol/L
Albumin	Conventional	<2.5 g/dL	
	SI	<25 g/L	
Total protein	Both	<0.8x LLN	>1.2x ULN
Creatinine	Conventional		>2.0 mg/dL
	SI		>177 μmol/L
Blood urea nitrogen	Conventional		>30 mg/dL
	SI		>10.7 mmol/L
Sodium	Conventional	<130 mEq/L	>150 mEq/L
	SI	<130 mmol/L	>150 mmol/L
Potassium	Conventional	<3.0 mEq/L	>6.0 mEq/L
	SI	<3.0 mmol/L	>6.0 mmol/L
СРК	Both		>5x ULN
Glucose	Conventional	< 50 mg/dL	>350 mg/dL
	SI	< 2.8 mmol/L	>19.4 mmol/L

ALT=alanine aminotransferase, AST=aspartate aminotransferase, CPK=creatine phosphokinase, GGT=γ-glutamyl transferase, LLN=lower limit of normal, ULN=upper limit of normal.

Parameter	Unit	Lower Criteria	Upper Criteria
Pulse	bpm	<50	>120
Systolic blood pressure	mm Hg	<85	>180
Diastolic blood pressure	mm Hg	<50	>110
Body temperature	°C	< 35.6	>37.7

Appendix B Criteria for Abnormal Changes from Baseline of Vital Signs

Appendix C Criteria for Identification of Markedly Abnormal Orthostatic Changes

Parameter	Criteria
Orthostatic Hypotension	(Orthostatic Systolic Blood Pressure < -20 mm Hg OR
	Orthostatic Diastolic Blood Pressure < -10 mm Hg) AND Heart Rate Increase > 20 beats/min

Note: Orthostatic measurement = standing vital measurement – supine vital measurement.

Parameter	Lower Criteria	Upper Criteria
Heart rate	< 50 beats per minute	>120 beats per minute
PR	≤80 milliseconds	≥200 milliseconds
QT Interval	≤300 milliseconds	≥460 milliseconds
QTcB Interval	≤300 milliseconds	≥500 milliseconds OR
		≥30 milliseconds change from baseline and ≥450 milliseconds
QTcF Interval	≤300 milliseconds	≥500 milliseconds OR
		≥30 milliseconds change from baseline and ≥450 milliseconds
QRS	≤80 milliseconds	≥180 milliseconds

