- 20. The subject has received TAK-831 in a previous clinical study; or has previously or is currently participating in this study; has received treatment with other experimental therapies within the preceding 60 days or <5 half-lives prior to randomization, whichever is longer; has participated in 2 or more clinical studies within 12 months prior to screening; or has participated in a clinical study for a psychiatric condition that is exclusionary per this protocol.
- 21. The subject is known by history or subject reporting to be currently infected or to have been infected with human immunodeficiency virus (HIV).
- 22. The subject has a known hypersensitivity to any component of the formulation of TAK-831 or to the practice pills (ie, small candies) used during the compliance monitoring device training.
- 23. The subject has a history of cancer. As an exception, subjects may be enrolled if they have a history of treated basal cell carcinoma, stage I squamous cell skin cancer, or in situ cervical cancer that has been in remission for ≥5 years prior to first dose of study drug.
- 24. Subjects with evidence or history of current clinically significant cardiovascular disease, including uncontrolled hypertension (supine diastolic blood pressure >95 mm Hg and/or supine systolic blood pressure >160 mm Hg, with or without treatment), symptomatic ischemic heart disease, uncompensated heart failure or recent (past 12 months) acute myocardial infarction or bypass surgery. Controlled essential hypertension and nonclinically significant sinus bradycardia and sinus tachycardia will not be considered significant medical illnesses and would not exclude a subject from the study.
- 25. The subject has a QT interval with Fridericia correction method (QTcF) >450 msec (males) or >470 msec (females), confirmed with 1 repeat testing, at screening or Day 1, or the subject has long QT syndrome or is under the treatment with Class 1A (eg, quinidine, procainamide) or Class 3 (eg, amiodarone, sotalol) antiarrhythmic drugs.

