9.1.19 ECG Procedure

A standard 12-lead ECG will be recorded. The following parameters will be recorded electronically by a central reader from the subject's ECG trace: heart rate, RR interval, PR interval, QT interval, QRS interval and QTcF. The central reader will interpret the ECG using 1 of the following categories: within normal limits or abnormal. If interpreted as abnormal, the investigator will assess the findings as either abnormal clinically significant, or abnormal not clinically significant. The interpretation of the ECG will be recorded in the source documents and in the eCRF. ECG traces recorded on thermal paper will be photocopied to avoid degradation of the trace over time. Requirements for the ECG equipment and procedure for collecting and transferring information to the central reader will be provided in the study reference manual

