ECG MAVs, identified by the criteria defined in Appendix D, will be tabulated. If a subject has a MAV for a particular 12-lead ECG parameter, all visits for that subject for that parameter will be listed. The number and percentage of subjects with at least 1 postdose markedly abnormal 12-lead ECG measurement will be summarized. The mapping of the subjects who meet the MAV criteria will be listed as a table. All observations, including ones at unscheduled visits, will be included in the MAV evaluation and summaries.

Overall ECG interpretation category (normal, abnormal not clinically significant, abnormal clinically significant) is collected by eCRF at baseline and at each scheduled post-baseline visit. Shifts in ECG interpretation will be presented as cross-tabulations (baseline versus each post-baseline visit) of numbers of subjects with normal, abnormal not clinically significant, and abnormal clinically significant interpretations with missing, if applicable, and total categories by regimen.

TAK-831-2002	Page 24 of 30
Statistical Analysis Plan Amendment No. 1	01 February 2021

Listings of all 12-lead ECG data will be provided in Appendix 16.2. MAVs will be flagged in the listings. The listing will include site number, subject identifier, age, gender, treatment group, study visit, and sample collection date.

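### QTcF rises of 30 ms or more that end below 450 ms are left out of the markedly abnormal ECG count, and no other table counts subjects by size of QTcF change

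*SAP*

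**What the plan says.** The ECG safety endpoint in SAP 5.1.3 is "Percentage of subjects who meet the markedly abnormal criteria for safety electrocardiogram (ECG) parameters at least once postdose". SAP 7.12.4 puts it into practice: "ECG MAVs, identified by the criteria defined in Appendix D, will be tabulated". It adds the number and percentage of subjects with at least one such value after dosing, and it includes unscheduled ECGs in that evaluation.

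For QTcF, and identically for Bazett QTc (QTcB), the Appendix D criteria table sets the upper limit as "≥500 milliseconds OR" a joint condition, "≥30 milliseconds change from baseline" together with a value of at least 450 ms. Uncorrected QT has an upper limit of "≥460 milliseconds" with no change condition. Heart rate is flagged below 50 or above 120 bpm.

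Apart from this count, SAP 7.12.4 plans N, mean, SD, median, minimum and maximum of the values and of the change from baseline. These use scheduled ECGs within 3 days of study drug. It also plans shift tables of the overall ECG interpretation, and listings of all ECG data. No table groups subjects by the size of their QTcF change.

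Protocol 9.1.19 names the recorded parameters as "heart rate, RR interval, PR interval, QT interval, QRS interval and QTcF". Protocol Appendix A schedules ECGs at screening, Day 1 and Day 84/ET, so there is one scheduled postdose ECG per subject. Protocol 13.1.7.4 identifies the criteria as the sponsor's own.

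**The concern.** The joint condition makes the rise needed for a flag depend on where the subject starts. A subject with a low baseline can have a much larger rise than a flagged subject and still not enter the count. Because no other table counts subjects by size of rise, a reader of the safety tables cannot see how many subjects per arm had a material QTcF increase.

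The other displays do not fill the gap. The minimum and maximum each describe one subject. The mean is diluted by unaffected subjects. Listings give no comparison between arms. A minority of subjects with rises that stay below 450 ms could therefore go unnoticed in the by-arm comparison.

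A smaller point concerns the same endpoint. SAP 7.12.4 does not say that the flags will be shown by parameter. QTcB and uncorrected QT can be flagged by heart rate alone, and in a pooled count such flags cannot be told apart from QTcF flags.

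**Working it through.** The documents give no computed figure on this point, so there is none to reproduce. They also give no QTcF distribution. Every distributional input below is an assumption.

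**1. The rule.** Let B be baseline QTcF. The joint condition needs a rise of at least max(30, 450 - B). The 500 ms limit adds nothing for a subject within the entry limits (Protocol 7.2: 450 ms for men, 470 ms for women): reaching 500 takes a rise of at least 500 - 470 = 30 ms and ends above 450.

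| Baseline QTcF (ms) | 370 | 380 | 390 | 400 | 410 | 420 or more |
|---|---|---|---|---|---|---|
| Smallest rise counted (ms) | 80 | 70 | 60 | 50 | 40 | 30 |

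So 370 to 445 ms (+75) is not counted, and 420 to 450 ms (+30) is.

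**2. Share counted if every subject rose by a fixed R.** This is P(B ≥ 450 - R). Assumed: B normal, mean 395-425 ms, SD 15-25 ms, cut off at 450 ms.

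| R (ms) | 30 | 40 | 50 | 60 | 80 |
|---|---|---|---|---|---|
| Share counted | 5-61% | 16-83% | 37-95% | 57-99% | 84-100% |

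**3. Share counted with measurement variation.** Baseline = T + e0 and postdose = T + 30 + e1, where e0 and e1 have the within-subject SD shown. The baseline SD includes that variation, and baselines above 450 ms are removed. Share caught = flagged / rising by at least 30 ms (simulated).

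| Baseline mean, SD (ms) | Within-subject SD 9 ms | Within-subject SD 12 ms |
|---|---|---|
| 400, 20 | 11.0 / 50.2 = 22% | 12.0 / 50.3 = 24% |
| 405, 18 | 14.1 / 50.2 = 28% | 15.5 / 50.3 = 31% |
| 410, 18 | 19.4 / 50.5 = 38% | 21.2 / 50.5 = 42% |
| 420, 18 | 31.2 / 51.4 = 61% | 33.8 / 51.8 = 65% |

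In an arm of 52 at baseline means of 400-410 ms, about 26 subjects would rise by 30 ms or more. The table would show about 6 to 11 (52 × 0.110 = 5.7; 52 × 0.212 = 11.0).

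**4. Noise in a change-only count.** With no drug effect, the SD of change is 9√2 = 12.7 ms or 12√2 = 17.0 ms. Then P(change ≥ 30) = P(Z ≥ 2.36) = 0.9%, or P(Z ≥ 1.77) = 3.9%. The placebo arm shows this background directly.

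**5. What the mean-change table would show.** With 85% of 52 = 44.2 active and 85% of 78 = 66.3 placebo completers, the standard error of the difference is 12.7 × √(1/44.2 + 1/66.3) = 2.5 ms. A uniform shift of 30 ms is about 12 standard errors.

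**6. Heart rate alone, with QTcF unchanged** (RR = 60/HR in seconds).
- QTcB = QTcF × RR^(-1/6). At QTcF 415 ms, moving from 60 to 100 bpm takes QTcB from 415 to 415 × 0.6^(-1/6) = 452 ms (+37). This is flagged.
- QT = QTcF × RR^(1/3). At 50 bpm and QTcF 433 ms, QT = 433 × 1.2^(1/3) = 460 ms. This is flagged.

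Neither rate meets the plan's own heart-rate criterion. Other cases need larger swings: from 60 bpm at QTcF 400 ms, QTcB is flagged only at 122 bpm, where heart rate is already flagged.

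**The case against.** The criteria are the sponsor's prespecified standard. Requiring both a change and a raised value is a reasonable way to keep a markedly abnormal category specific. That stands, and it is why the remedy should add to the criteria rather than replace them.

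A reader might infer that most subjects with large rises are never counted. The documents do not support this. They give no baseline distribution, and the answer turns on what counts as large: most rises of exactly 60 ms are counted in every scenario of step 2. For observed rises of at least 60 ms, simulations over wider assumptions (baseline means 400-420 ms, mean shifts 0-30 ms) gave 18-86%, on both sides of one half. Nor are the rises lost altogether. They enter the change statistics if scheduled and within 3 days of study drug, and they are always listed. Changes judged clinically significant are recorded as adverse events (Protocol 10.1.3).

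A reader might also infer that one scheduled postdose ECG leaves no second chance of a flag. SAP 7.12.4 includes unscheduled ECGs in the count, so that goes too far.

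The uniform 30 ms shift in step 3 would be plain from the mean change (step 5). That is correct. The simulation measures how sensitive the count is, not whether the trial would miss such a shift. What the plan shows poorly is a minority of subjects with rises and little movement in the mean.

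Finally, a reader might conclude that QTcB and uncorrected QT should leave the endpoint. The documents do not require that. The endpoint covers ECG parameters generally, uncorrected QT is a recorded parameter, QTcB can be derived from the recorded QT and RR, and Protocol 13.1 leaves the definition of analysis variables to the SAP.

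**Conclusion.** The point holds in a limited form. It is certain from the text that a QTcF rise of 30 ms or more ending below 450 ms is outside the markedly abnormal count, and that no other by-arm count of subjects by size of QTcF change is planned.

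The share missed is not certain. Under the step 3 assumptions the rule misses roughly 58-78% of rises of 30 ms or more at baseline means of 400-410 ms, and roughly 35-39% at 420 ms. These figures assume normal distributions, a 30 ms mean shift and a single 450 ms cap on baseline, although women may enter at up to 470 ms. Whether most such rises are missed therefore depends on the baseline mean.

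That QTcB and uncorrected QT can be flagged by heart rate alone is true in principle, but it needs a sizeable change in rate or a rate near the plan's own limits. It supports separate display, not removal.

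This is a low-cost improvement to a safety table. It does not affect efficacy inference, sample size or trial conduct.

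**What to change.** In SAP 7.12.4 and Appendix D, keep the existing criteria and make two additions.

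- By arm, give the number and percentage of subjects with a postdose QTcF increase from baseline of at least 30 ms, and of at least 60 ms, whatever the final value. Use all postdose observations, including unscheduled ones, as the markedly abnormal count already does. The 30 ms cut is the plan's own trigger. The 60 ms cut is twice that trigger and is a proposal, not a figure from the documents.
- Show the markedly abnormal counts separately for each ECG parameter, so that QTcF flags can be told apart from QTcB and uncorrected QT flags.

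The cost is a few extra table rows and minor programming on data already collected. The 30 ms row will contain some chance rises, about 1-4% of subjects under the assumptions in step 4, so it should be read against placebo.
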